- 7. To assess the effects of rosuvastatin 10 mg and 20 mg in combination with ezetimibe 10 mg vs the same dose of rosuvastatin 10 mg and 20 mg alone on percentage change in LDL-C, HDL-C, TC, TG, nonHDL-C, ApoB, ApoA-I; TC/HDL-C, LDL-C/HDL-C, nonHDL-C/HDL-C, ApoB/ApoA-I and hs-CRP from baseline and on current American and European guideline lipid goal achievement after 6 weeks monotherapy and 6 weeks of combination therapy (mean value of 4 and 6 weeks of combination therapy will be used)
- 8. To assess the safety and tolerability of rosuvastatin in combination with ezetimibe vs simvastatin in combination with ezetimibe by observing adverse events, changes in laboratory safety variables and discontinuations over 6 weeks of combination therapy

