6.3 Description of analysis sets

Efficacy analyses will be performed on intent-to-treat (ITT) last observation carried forward (LOCF), completers only and observed data. Per-protocol (PP) data will be available for subsequent analysis if required, though this is not anticipated.

The ITT population will consist of patients who have baseline and at least 1 post-baseline measurement.

LOCF will be interpreted as follows:

- If no data are available for a particular variable following commencement of therapy, then for that variable, the patient is not included in the ITT analysis
- If a measurement is not available for either Visit 4 or 5 (after 4 and 6 weeks of monotherapy, respectively), then the LOCF for the monotherapy phase will be determined as the last of the on-monotherapy measurements
- If a measurement is not available for either Visit 6 or Visit 7 (after 4 and 6 weeks of combination therapy, respectively), then the LOCF for combination therapy will be determined as the last of the on-combination therapy measurements
- In the case where there are no measurements available in the combination therapy phase, then the monotherapy LOCF will be carried forwards to impute the combination therapy LOCF

Completers are the patients in the ITT population who have had at least 1 measurement made following combination therapy. An analysis of completers will be done specifically to show combination treatment efficacy in the absence of dilution of effect, due to carryover of LOCF data from the monotherapy phase.

Patients will be evaluated using randomised treatment.

There will be 2 safety populations. The dietary lead-in safety population will consist of all patients who entered the dietary lead-in period. The randomised safety population will consist

of all patients who were randomised and took at least 1 dose of study medication. Patients in this safety population will be analysed by treatments and doses actually received as follows:

Period	Treatments
Dietary lead-in	Diet
Randomised (0 to 12 weeks)	Rosuvastatin or simvastatin monotherapy followed by combination therapy of rosuvastatin or simvastatin with ezetimibe

Table 6Safety populations

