Analysis of hs-CRP will be performed using the non-parametric Kruskal-Wallis test (Hollander and Wolfe 1973). The median score will be used. In the case of pairwise comparisons, a Wilcoxon test will be used.

Lipid data will be analysed geometrically (log transformed). This transformation is preferred for the following reasons:

- Experience with similar data in the EXPLORER study shows that the change in LDL-C data has a rightward skew that increases in severity with increasing treatment efficacy
- A study of STELLAR data found that the arithmetic mean of percentage change from baseline produced estimates of efficacy that were consistently below the median effect. The geometric mean was much closer to the median
- Information collated from other studies suggests that ezetimibe has a multiplicative effect on LDL-C. This effect is better modelled by a geometric analysis
- A Bootstrap analysis of EXPLORER data showed that use of the geometric analysis provided equivalent power to the percentage change from baseline analysis with approximately 30% fewer subjects

AEs can occur in the dietary lead-in phase and the randomised phase of the study. All AEs will be classified according to the following:

- Treatment emergent. This is further categorised as:
 - Ongoing from the dietary lead-in period and subsequently worsening during the randomised period, and;
 - Starting during the randomised period

All AEs will be categorised by body system and MedDRA preferred term and listed for each patient. In the randomised safety population, treatment emergent events will be reported as frequencies in each treatment group. Frequencies of AEs leading to withdrawal from the randomised period will also be tabulated and reported by treatment group. AEs leading to death, SAEs and drug-related AEs and SAEs will be presented similarly. Tests of statistical significance will not be performed.

Haematology and clinical chemistry data will be listed for each patient and summarised for each treatment group at each visit. Values outside laboratory reference ranges will be highlighted.

Shift tables for haematuria and proteinuria data will show numbers and percentages of patients with categories of urinary protein and blood (none, trace, +, ++, +++ and ++++) at Week 12 against baseline (Week 0) and Visit 5 (Week 6).

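### Safety objective 8 covers the six combination weeks, but adverse event frequencies are specified only for the whole 12-week randomised period

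*Protocol*

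**What the plan says.** Secondary objective 8 (Protocol, Section 2.2, repeated in the synopsis) is "To assess the safety and tolerability of rosuvastatin in combination with ezetimibe vs simvastatin in combination with ezetimibe by observing adverse events", followed by "changes in laboratory safety variables and discontinuations over 6 weeks of combination therapy". Ezetimibe is added at Visit 5, Week 6 (Section 3.4.2), so the objective's period is Weeks 6 to 12.

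The analysis sections set a different frame:

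- **Population (6.3):** the randomised safety population consists "of all patients who were randomised and took at least 1 dose of study medication". Reaching the combination phase is not required.
- **Period (6.3, Table 6):** one randomised row, Weeks 0 to 12, with the treatment given as "Rosuvastatin or simvastatin monotherapy followed by combination therapy of rosuvastatin or simvastatin with ezetimibe".
- **Treatment-emergent (6.4):** either carried over from the dietary lead-in and worsening after randomisation, or "Starting during the randomised period". The only dividing line is randomisation.
- **Tabulation (6.4):** "In the randomised safety population, treatment emergent events will be reported as frequencies in each treatment group". For withdrawals due to AEs: "Frequencies of AEs leading to withdrawal from the randomised period will also be tabulated and reported by treatment group". Deaths, serious AEs and drug-related events are to be presented in the same manner.

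**The concern.** Followed as written, the AE tables describe the 12-week treatment sequence, while the objective asks about the combination phase. An event in Week 2 on statin alone and an event in Week 8 on statin plus ezetimibe fall into the same cell. A patient who leaves before Visit 5 counts in the denominator without having taken ezetimibe.

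At stake is the descriptive reading of combination safety. Section 6.5 notes that these rosuvastatin/ezetimibe combinations had not been studied in large populations. Section 3.2.2 acknowledges that statin treatment starts at high doses, so some events may be linked to starting the statin and fall in the first six weeks. If both arms carry such a background, a contrast that emerges after ezetimibe is added becomes harder to see in the only AE tables the protocol specifies.

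**Working it through.** **1. Objective against analysis, component by component**

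| Component of objective 8 | Specified summary | Separable at Week 6? |
|---|---|---|
| AEs, serious AEs, drug-related AEs, AEs leading to death | Frequency per arm, Weeks 0 to 12 (6.3, 6.4) | No |
| AEs leading to withdrawal | Frequency per arm, randomised period (6.4) | No |
| Haematology and chemistry | Summarised per arm at each visit (6.4) | Yes |
| Urine protein and blood shifts | Week 12 against Week 0 and against Week 6 (6.4) | Yes |
| Withdrawals and reasons | Numbers withdrawn at each visit, per arm (6.3.1) | Yes |

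The mismatch is confined to the first two rows.

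**2. Dilution (assumed rates)**

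The protocol gives no AE rate and no safety sample size, so there is no figure to reproduce. Let m and c be the proportions of patients with an event in the monotherapy and combination phases. Take the phases as independent and assume everyone enters both. Then:

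12-week incidence = 1 − (1 − m)(1 − c)

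Suppose two arms share the same m and have c = 20% and 10%, a ratio of 2.0 and a difference of 10 points.

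- m = 20%: 1 − 0.8 × 0.8 = 36% vs 1 − 0.8 × 0.9 = 28%. Ratio 1.29, difference 8 points.
- m = 30%: 1 − 0.7 × 0.8 = 44% vs 1 − 0.7 × 0.9 = 37%. Ratio 1.19, difference 7 points.

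**3. Share of affected patients whose first event is on monotherapy**

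Share = m / [1 − (1 − m)(1 − c)]

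| m | c | 12-week incidence | Share |
|---|---|---|---|
| 20% | 20% | 36% | 0.20/0.36 = 56% |
| 30% | 20% | 44% | 0.30/0.44 = 68% |
| 30% | 15% | 40.5% | 0.30/0.405 = 74% |
| 20% | 30% | 44% | 0.20/0.44 = 45% |

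Over these assumed values the share runs from 45% to 74%.

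**4. Denominator**

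Section 6.5 plans about 200 randomised per arm and 10% dropout after randomisation: 0.10 × 200 = 20 patients. If all of it occurs before Visit 5, 20 of 200 per arm have no ezetimibe exposure. If all of it occurs later, the number is 0. The protocol does not say how dropout divides between the phases, so 20 is an upper bound.

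**The case against.** **The 12-week table is a sound analysis.** Section 3.2.1 says there is one randomisation, to the treatment sequence. Counting every event from randomisation preserves that comparison, whereas a combination-phase set depends on who got through monotherapy. This stands, and it is why the 12-week table should stay.

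**The tables are not labelled as combination safety.** A reader might infer that the plan counts monotherapy events as combination-therapy events. The protocol does not say so: Table 6 names both phases and 6.4 reports by treatment group. The difficulty arises only when these tables are used to answer objective 8, for which no other AE table is specified.

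**Much of objective 8 is already separable.** A reader might also infer that the combination contrast cannot be read at all. That goes too far, because laboratory data, urinalysis shifts and withdrawals can be split at Week 6.

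**The statistical analysis plan may add a phase split.** It may, since onset dates are collected (4.7.1.2) and all AEs are listed by patient (6.4). However, the protocol does more than leave the period open: it fixes a safety period and population that differ from those of its own objective. Section 6.3 does say that the safety population is analysed by treatment actually received, but the table that follows has only one randomised row, so this does not separate the phases.

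**The consequences are limited.** Section 6.4 rules out significance tests on AEs, so no error rate or efficacy result is touched. This stands.

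**Conclusion.** The point holds for the tables of AEs, serious AEs and AEs leading to withdrawal. None of those specified matches the period in objective 8 or is restricted to patients exposed to ezetimibe, and pooling the phases would dilute a difference confined to the combination phase.

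The size is illustrative. A ratio of 2.0 falls to 1.29 or 1.19 if monotherapy incidence is 20% or 30% in both arms, with independent phases and no dropout. Lower monotherapy incidence would dilute less. If monotherapy incidence differs between arms, the 12-week contrast would also carry that difference. It may be tempting to say that half of all tabulated events must come from monotherapy because 6 of 12 weeks do. That requires a constant event rate, which the protocol does not support. Likewise, 20 unexposed patients per arm is the extreme case and should not be read as an expectation.

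The effect is on description and interpretation only, and the data for a remedy will exist.

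**What to change.** In Sections 6.3 and 6.4:

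1. Keep the 0 to 12 week tables as the randomised comparison of treatment sequences.
2. Add tables of AEs, serious AEs and AEs leading to withdrawal with onset or worsening on or after the first combination-therapy dose. Use patients who took at least one combination dose as the denominator.
3. State beside these tables that the set is conditional on completing monotherapy, so the arms compared are no longer exactly those randomised.

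Alternatively, reword objective 8 to cover the safety of the 12-week sequence. That removes the mismatch but gives up a specified AE summary for the combination phase.

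The first option costs a few more tables from onset dates already collected. Worsening across Week 6 can follow the same rule that the plan needs for events carried over from the dietary lead-in. The second option costs only a change of wording in Section 2.2 and the synopsis. Neither affects sample size, visits or the efficacy analyses.

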3.3.5.2 Procedures for discontinuation

Patients who discontinue should always be asked about the reason(s) for their discontinuation and about the presence of any AEs. If possible, they should be seen and assessed by an Investigator(s) and the patient followed according to the study schedule. AEs should be followed-up to obtain a final outcome. Serious adverse events (SAEs) should be followed-up until resolution or until stabilised and no further change is expected. All investigational products (IPs) should be returned to the clinic by the patient.

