4.7.2 Laboratory safety measurements and variables

4.7.2.1 Methods of assessment

Clinical chemistry testing will be performed at Visits 1, 3, 5 and 7 (Weeks -6, 0, 6 and 12) and will include: albumin, total bilirubin, blood urea nitrogen, CK, serum creatinine, ALT (SGPT), aspartate aminotransferase (AST) (serum glutamic oxaloacetic transaminase

(SGOT)), fasting glucose, alkaline phosphatase, calcium, phosphate, potassium, sodium, total protein and gamma-glutamyl transferase (GGT). At Visits 2, 4 and 6 (Weeks -2, 4 and 10) abbreviated clinical chemistry tests will be performed, consisting of: CK, serum creatinine, ALT, AST and TSH (TSH only at Visit 2 (Week -2)).

Haematology testing will be performed at Visits 1, 3, 5 and 7 (Weeks -6, 0, 6 and 12), which will include: platelet count, haemoglobin, haematocrit, red blood cell (RBC) count, RBC indices (mean cell volume (MCV), mean cell haemoglobin (MCH), mean cell haemoglobin concentration (MCHC)), white blood cell (WBC) count, WBC differential (neutrophils, bands, lymphocytes, monocytes, eosinophils, basophils).

A 10 mL mid-stream urine sample will be collected at Visits 3, 4, 5, 6 and 7 (Weeks 0, 4, 6, 10 and 12) for analysis at the central laboratory. For Visits 3, 5 and 7 (Weeks 0, 6 and 12), urinalysis sample is to consist of: visual description (colour and appearance), a dipstick test (specific gravity, pH, protein (qualitative), glucose, ketones, bilirubin and blood), microscopy (RBC, WBC, bacteria, casts and crystals). For Visits 4 and 6 (Weeks 4 and 10), the following abbreviated urinalysis is to be performed: a dipstick test (specific gravity (if suspected/necessary), protein (qualitative) and blood). At Visits 4 to 7 (Weeks 4 to 12), for any patients with dipstick protein ++ or greater where this represents $a \ge 1$ grade shift (eg, from + to ++ or trace to ++) from the baseline visit, the central laboratory will automatically perform a quantitative assessment of total protein, albumin and creatinine.

If the urine protein/creatinine ratio is >0.5 mg protein per mg creatinine (US) or >56 mg protein per µmol creatinine (RoW), the Investigator may stop study medication following consultation with the relevant AstraZeneca personnel (eg, Clinical Study Team Physician).

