Appendix Date							

Appendix F Management of Increased Urine Protein on Dipstick

Clinical Study Protocol Appendix F Drug Substance Rosuvastatin Study Code D356FC00003 Appendix Edition Number 1.0 Appendix Date

GUIDANCE ON THE MANAGEMENT OF INCREASED URINE PROTEIN FOLLOWING DIPSTICK TEST

- A urinalysis will be performed at Visits 3 to 7.
- If the urine dipstick protein is increased from the baseline value, the Investigator should evaluate the patient for any potential cause.
- At Visits 4 to 7, for all patients with a urine dipstick protein of ++ or greater, where this represents $a \ge 1$ grade shift (eg, from + to ++ or trace to ++), the central laboratory will automatically perform quantitative assessment of total protein, albumin and creatine.

If the urine protein/creatinine ratio is >0.5 mg protein per mg creatinine (US) or >56 mg protein per μ mol creatinine (Rest of World), the Investigator may stop study medication following consultation with the relevant AstraZeneca personnel, eg, the Clinical Study Team Physician.

Clinical Study Protocol Appendix G						
Drug Substance	Rosuvastatin					
Study Code	D356FC00003					
Appendix Edition Number	1.0					

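### The urine protein and blood shift tables use Week 12 as their only outcome visit, so positives confined to Week 4 or Week 10, and patients with no Week 12 sample, enter neither table

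*Protocol*

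**What the plan says.** Section 4.7.2.1 sets the sampling: "A 10 mL mid-stream urine sample will be collected at Visits 3, 4, 5, 6 and 7 (Weeks 0, 4, 6, 10 and 12"). The full urinalysis is done at Weeks 0, 6 and 12. At Weeks 4 and 10 an abbreviated version is used, and its dipstick still reads protein and blood. The same section and Appendix F make the result actionable throughout treatment: "At Visits 4 to 7 (Weeks 4 to 12), for any patients with dipstick protein ++ or greater", where this is a rise of at least one grade, the central laboratory quantifies protein automatically. If the protein/creatinine ratio is then above a stated limit, "the Investigator may stop study medication following consultation with the relevant AstraZeneca personnel".

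Section 6.4 fixes the analysis, and the synopsis repeats it: "Shift tables for haematuria and proteinuria data will show numbers and percentages of patients with categories of urinary protein and blood", "at Week 12 against baseline (Week 0) and Visit 5 (Week 6"). The sentence before it promises patient listings and by-visit summaries for haematology and clinical chemistry and does not name urinalysis. No worst-value or last-on-treatment category is given, and no rule for a missing Week 12 sample.

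For patients who discontinue, section 3.3.5.2 asks that they be seen if possible and "the patient followed according to the study schedule".

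**The concern.** The protocol reads the dipstick at four on-treatment visits and acts on it at each of them, but both tables take their outcome from one visit only. A transient ++ at Week 4 or Week 10 can set off the protocol's own quantification step and leave no trace in the tables.

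The finding being measured is also a permitted reason to stop drug. A patient who stops for it may have no Week 12 sample, or one taken off drug, so the tables are selective in the direction of looking cleaner. Section 3.2.2 names renal abnormality as a known risk of this drug class, section 6.2 lists urinalysis among the safety variables, and secondary objective 8 covers changes in laboratory safety variables. What is at stake is whether the stated urine display describes what happened on treatment.

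**Working it through.** **Inputs from the protocol.** On-treatment dipsticks at Weeks 4, 6, 10 and 12 (4.7.2.1). 200 randomised per arm and 10% dropout after randomisation (6.5). The protocol states no dipstick-positive rate, so it has no figure of its own to reproduce here.

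**Who appears where.**

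| Patient | Week 0 to Week 12 table | Week 6 to Week 12 table |
|---|---|---|
| Positive only at Week 4 or 10 | shown as no shift | shown as no shift |
| Positive at Week 6, negative at Week 12 | shown as no shift | visible through the Week 6 category |
| Positive at Week 12 | visible | visible |
| No Week 12 sample | absent | absent |
| Stopped, followed to Week 12 | off-drug value | off-drug value as outcome |

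**Missing samples.** If nobody who drops out is followed, 200 × 0.10 = 20 per arm (80 of 800) lack a Week 12 dipstick. Suppose 4 of 200 reach ++ (2.0%) and remain positive while observed. If 2 of them stop with no Week 12 sample, the table shows 2/180 = 1.1%. If all 4 do, it shows 0/180.

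**Transient positives, independent visits, nobody missing.** Let p be the assumed chance of ++ at a visit.
- Ever positive per 200: 200 × [1 − (1 − p)^4] = 7.9, 15.5 and 22.9 for p = 1%, 2% and 3%.
- Positive at Week 12: 200p = 2, 4 and 6.
- Positive at Week 6 but not Week 12, so visible in the second table: 200p(1 − p) = 2.0, 3.9 and 5.8.
- In neither table: 200 × [1 − (1 − p)²](1 − p)² = 3.9, 7.6 and 11.1.

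The share in neither table is 3.9/7.9, 7.6/15.5 and 11.1/22.9, all 48% to 49%, so it barely depends on p in this range.

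**Adding persistence and 10% missing at Week 12.** Here p = 1%, grades are correlated across visits through a latent normal variable, and missingness is unrelated to the dipstick result (simulation, checked again for this note).

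| Latent correlation | Ever positive per 200 | In neither table |
|---|---|---|
| 0 | 7.9 | 55% |
| 0.5 | 6.7 | 50% |
| 0.8 | 4.9 | 41% |
| 0.95 | 3.4 | 29% |
| 1 (fully persistent) | 2.0 | 10% |

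The first row by hand: seen in either table = 0.9 × (1 − 0.99²) = 0.0179; ever positive = 1 − 0.99⁴ = 0.0394; 1 − 0.0179/0.0394 = 55%. In the last row, only the missing Week 12 samples are lost.

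**Combination phase only.** Objective 8 covers the combination phase, so the relevant losses are Week 10 positives resolved by Week 12 and missing or off-drug Week 12 samples. With independent visits, p = 1% and 10% missing, 200 × (1 − 0.99²) = 3.98 patients are positive at Week 10 or 12, and the Week 12 column shows 200 × 0.9 × 0.01 = 1.8, a loss of 1 − 1.8/3.98 = 55%. With full persistence the loss is 10%.

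**The case against.** A reader might infer that patients who stop for proteinuria vanish from the renal safety result. The documents do not support that. Treatment-emergent adverse events and those leading to withdrawal are tabulated by arm (6.4). Withdrawals with reasons are summarised by visit and arm (6.3.1). Marked laboratory abnormalities are an example of events given a narrative (4.7.1.1). Creatinine is measured at every visit, and clinical chemistry is summarised by visit. These are partial substitutes: Appendix E requires an adverse event when drug is stopped for creatinine, but Appendix F has no matching sentence for urine protein.

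Three further limits stand. Week 6 positives with a Week 12 sample are visible in the second table. Stopping is optional, needs a raised ratio rather than the ++ shift alone, and does not by itself remove a patient, because follow-up to schedule is requested. Positives at Weeks 4 and 6 arise on monotherapy, outside objective 8, for which the Week 6 to Week 12 table covers the right phase.

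It is also tempting to say that the comparison between arms is biased. Nothing in the documents shows that stopping or missing samples would differ by arm, so that remains a possibility only.

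Finally, a SAP not shown here may add worst-value tables, and nothing in 6.4 forbids them. But 6.4 does not leave the matter open: it names a specific display with a specific outcome visit, and a better one is available from the same data.

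**Conclusion.** The point holds in limited form. The only urinalysis display that the protocol fixes misses positives confined to Week 4 or Week 10 and patients without a Week 12 sample. It takes an off-drug value from those followed after stopping, and it gives no Week 0 to Week 6 shift on monotherapy. It can understate on-treatment proteinuria and haematuria. How far is unknown: the 30% to 55% range rests on an assumed 1% per-visit rate, 10% lacking a Week 12 sample, missingness unrelated to the result, and latent correlation between 0 and 0.95. With full persistence the loss falls to the share missing at Week 12. The loss would grow if positive patients were more likely to lack that sample. This concerns a descriptive safety display, not the primary endpoint, and is a worthwhile low-cost improvement.

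**What to change.** In 6.4 and the synopsis, add shift tables for urine protein and blood from Week 0 to the worst on-treatment category, one for monotherapy (Visits 4 and 5) and one for combination therapy (Visits 6 and 7). Base them on the randomised safety population and include unscheduled samples and the last value before stopping. Add the number of patients per arm meeting the existing Appendix F ++ trigger at any visit. Keep the Week 12 tables. No change to sampling or to any stopping rule is involved.

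The cost is wording in two places and a small amount of table programming. The one downside is that worst-value tables also count one-off dipstick false positives, which is a reason to show them beside the Week 12 tables and not in their place.
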